9.5.6. Secondary Endpoints

All secondary endpoints will be presented with descriptive summary statistics. All data collected will be listed, together with derived variables. Graphical displays will show efficacy variables over time.

Descriptive statistical methods will be used to analyze all secondary efficacy data. In addition, summaries for certain subgroups if defined will also be presented. For time to event endpoints, survival curves will be estimated using the Kaplan-Meier time to event method. Summary statistics and summary plots will be presented for all other endpoints including other endpoints including CWS and AIS (as components of C-GTI) and the complementary GTI-SL, QoL, PK, PD, immunogenicity, and self-administration. More details for the analysis of the endpoints will be described in the SAP.

Analyses will not only refer to the baseline of ARGX-113-1905, but the baseline of ARGX1131904 will be used for specific analysis as stated in the SAP for this OLE trial.

More detailed descriptions will be presented in the SAP of the study.

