The recent approval of rituximab in PV adults has dramatically changed the mainstay of therapy of the disease, and is now approved as a first-line therapy in association with prednisone for moderate and severe cases. Rituximab is primarily used in patients with refractory PV who do not respond well to other treatments. However, the lack of long-lasting remission and great number of SAEs associated with prednisone and immunosuppressants has led researchers to develop alternative first-line treatments. Rituximab as second-line and third-line treatment (1 to 2 g per cycle) was shown to a induce long-term remission at a high rate, which could not be achieved by any other treatment (75% remission rate in PV after 1 year⁹). Flare rates after rituximab therapy ranged between 25% after 1 year up to 80% in long-term follow-up. Recent evidence has shown the efficacy of a first cycle of rituximab (2 g) as first-line treatment followed by new cycles (0.5 g) after 12 months and 18 months, in combination with lower doses of prednisone (0.5 to 1 mg/kg per day according to disease severity¹⁰). Using this first-line regimen, a higher proportion of complete remission after 2 years, ie, 89%, was demonstrated. Flare cases were observed to be also lower (24% after 2 years), a majority occurring within 6 to 12 months after the first cycle. A strong prednisone sparing effect, ie, by about two-thirds, was demonstrated.

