#### 4.1.3.2 TIME TO DC, CR, CRMIN AND CROFF

Time to DC, Time to CR, Time to CRmin and Time to CRoff will be descriptively presented with median times, quantiles and number and percentage of participants censored and with event, as obtained through Kaplan-Meier analysis.

The tables will be produced for PV participants and for all participants (PV+PF), also overall and by disease status at roll-over.

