#### 4.1.3.5 TIME TO FLARE AFTER CRMIN

Time to flare after CRmin will be descriptively presented with median times, quantiles and number and percentage of participants censored and with event, as obtained through Kaplan-Meier analysis.

The tables will be produced for PV participants and for all participants (PV+PF) who achieved CRmin, also overall and by disease status at roll-over.

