## 8. LIST OF TABLES, LISTINGS AND FIGURES

#### 8.1 TABLES

Note: tables to be produced for the topline results (TL) are indicated in last column

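### The protocol promises Kaplan-Meier curves and plots of efficacy over time; the SAP lists no figure, does not declare the omission, and leaves little to report on time to flare or CRoff if events are few

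*Protocol*

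**What the plan says.** Protocol 9.5.6 makes three statements about output for the secondary endpoints. On efficacy in general: "Graphical displays will show efficacy variables over time". On time to DC, CR, CRmin, CRoff and flare: "For time to event endpoints, survival curves will be estimated using the Kaplan-Meier time to event method". On the rest: "Summary statistics and summary plots will be presented for all other endpoints". It leaves further detail to the SAP. Protocol 9.1.1 allows minor changes of method without an amendment, provided the SAP documents them as changes from the protocol.

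SAP 4.1.3.2 says that the times to DC, CR, CRmin and CRoff "will be descriptively presented with median times, quantiles and number and percentage of participants censored and with event, as obtained through Kaplan-Meier analysis". SAP 4.1.3.5 has the same content for flare: "Time to flare after CRmin will be descriptively presented with median times, quantiles and number and percentage of participants censored and with event". Neither section mentions a plot, an event probability at a fixed week, or a confidence interval. SAP section 8 is headed "LIST OF TABLES, LISTINGS AND FIGURES", but it contains only 8.1 (tables) and 8.2 (listings), and the table of contents agrees. SAP 6.1 declares changed visit labels and two extra endpoints, and is silent on plots.

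SAP 4.1.3.1 and 4.1.3.4 do give exact 95% intervals for the proportions with CRmin, CRoff and flare after CRmin.

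**The concern.** There are two issues. The first is consistency: the protocol commits to graphical output, the SAP specifies none, and the change is not recorded where Protocol 9.1.1 says it should be.

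The second is what the remaining output can say. A Kaplan-Meier quantile exists only if the estimated curve falls far enough during follow-up. SAP 4.1.2.2 and 4.1.2.5 censor at the end of the treatment period or phase, so someone who reaches CRmin late has little time left in which a flare can be seen. If flares are uncommon, neither the median nor the lower quartile may exist. The reader is then left with the percentage with an event. That figure, like the exact intervals on the related proportions, treats a person watched for 12 weeks the same as one watched for 42. Time to CRoff has the same weakness if few participants come off prednisone. Protocol 4.2 singles out duration of CR and time to CRoff for specific evaluation, so these are results the trial intends to interpret.

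**Working it through.** **No planned figure to reproduce.** The documents give no sample size, power, event rate or expected number of events for these endpoints. The calculation below is illustrative.

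**Inputs for time to flare after CRmin in treatment period 1**
- Low rate: 25% at 1 year, the lower end in Protocol 2.2 ("Flare rates after rituximab therapy ranged between 25% after 1 year up to 80% in long-term follow-up").
- High rate: 45% within 6 months, reported in Protocol 2.2 for prednisone-treated patients.
- Assumed, not in the documents: constant hazard, CRmin reached uniformly between weeks 10 and 40, follow-up to week 52, and n = 20, 40 or 80 per table. Time at risk U is then uniform from 52 − 40 = 12 to 52 − 10 = 42 weeks.
- The SAP does not define its quantiles. I take the lowest to be 25%.

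**Hazards per week**
- Low: −ln(0.75)/52 = 0.00553
- High: −ln(0.55)/26 = 0.02299

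**True incidence at the longest time at risk, 1 − exp(−42λ)**
- Low: 20.7%. This is below 25%, so even the first quartile lies beyond follow-up. An estimate appears only through chance in the tail.
- High: 61.9%. The first quartile is at −ln(0.75)/0.02299 = 12.5 weeks and the median at ln(2)/0.02299 = 30.1 weeks, both within reach.

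**Simulated share of tables in which the quantile is estimable** (2000 tables per cell; a separate run of 3000 is in brackets where available)

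| Rate | Quantile | n = 20 | n = 40 | n = 80 |
|---|---|---|---|---|
| 25% per year | median | 4.3% (4.5%) | 1.4% (2.2%) | 1.5% (1.4%) |
| 25% per year | first quartile | 29.0% (29%) | 23.6% (25%) | 23.3% (22%) |
| 45% per 6 months | median | 69% (69%) | 79% (78%) | 87% (87%) |
| 45% per 6 months | first quartile | 99% | 100% | 100% |

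**What the crude percentage shows instead.** Its expected value is 1 − [exp(−12λ) − exp(−42λ)]/(30λ).
- Low: 1 − (0.9358 − 0.7927)/0.1660 = 13.8%, against a true 42-week risk of 20.7%.
- High: 1 − (0.7589 − 0.3807)/0.6898 = 45.2%, against 61.9%. Here the quantiles are usually available as well.
- With censoring uniform over weeks 4 to 52 instead, the crude figure at the low rate averages 14.1% against a true 52-week risk of 25%.

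**What a fixed-week estimate would show.** Take n = 60 and 25% incidence at week 52. The Kaplan-Meier event probability at week 24 averages 12.4%; the true value is 1 − exp(−24 × 0.00553) = 12.4%. The mean 95% interval width is 17 points with everyone followed to week 52, and 20 points with censoring uniform over weeks 4 to 52.

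**Which weeks the follow-up supports.** The share at risk t weeks after CRmin is P(U > t) × exp(−λt).

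| Week after CRmin | Low rate | High rate |
|---|---|---|
| 12 | 1.0 × 0.936 = 94% | 1.0 × 0.759 = 76% |
| 24 | 0.6 × 0.876 = 53% | 0.6 × 0.576 = 35% |
| 36 | 0.2 × 0.819 = 16% | 0.2 × 0.437 = 9% |
| 52 | 0 | 0 |

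Weeks 12 and 24 are usable. At week 36 a table of 20 would have about 2 to 3 people left, and at week 52 none.

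**The case against.** The strongest reply is that the SAP does what a descriptive extension needs. Protocol 9.2 tests no hypothesis, and Protocol 9.1.3 says efficacy will be presented in summary tables, which the SAP supplies. Neither document promises fixed-week probabilities or intervals for Kaplan-Meier quantities. Listings 16.2.6.1 and 16.2.6.2 hold the disease-status data, so curves could be drawn later. All of this stands and limits the point to a reporting gap; it does not explain why the promised plots went unlisted and undeclared.

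A reader might also infer more than the documents support:
- **That Kaplan-Meier has been dropped.** It has not. The planned medians and quantiles come from the Kaplan-Meier analysis; the conflict is over displaying the curve.
- **That figures are ruled out.** SAP 2.2.4 and 2.4.3 refer to figures in general layout rules. The accurate statement is that none is specified or listed.
- **That there are no confidence intervals.** The proportions for CRmin, CRoff and flare after CRmin have them. The Kaplan-Meier quantities do not, and DC and CR have no companion proportion.
- **That all five time-to-event endpoints become uninformative.** Nothing suggests that DC, CR or CRmin will be rare; Protocol 4.3 describes rapid DC in the phase 2 study.
- **That flare will be infrequent.** The 25% is the low end of a range for rituximab, whereas participants here are off efgartigimod after CRmin and may be tapering prednisone. Those who roll over in CRmin are timed from the roll-over visit. With 52 weeks at risk and no dropout, the first quartile is estimable in 45-58% of tables at the low rate, and the median in 98-100% at the high rate.

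**Conclusion.** The point holds as an undeclared gap between protocol and SAP, together with a limited but real loss of information. No error rate, sample size or decision rule is affected.

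The loss is conditional. It arises where cumulative incidence within the time at risk stays below the lowest quantile reported. That is plausible for flare after CRmin in treatment periods, and for CRoff if few participants stop prednisone; it is not shown for DC, CR or CRmin. The size depends on the assumed timing and borrowed rates: in treatment period 1 the median is nearly always missing at 25% per year and usually present at 45% per 6 months. The mechanism does not depend on those figures: the fewer the flares, the less the planned table can say, and the crude percentage that remains understates risk because follow-up is unequal.

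**What to change.** In SAP 4.1.3.2 and 4.1.3.5:
- Add Kaplan-Meier event probabilities with 95% confidence intervals and numbers at risk at prespecified weeks that the time at risk supports. After CRmin in a treatment period, weeks 12 and 24 are suitable examples. Use later weeks only where enough participants remain at risk, such as the roll-over phase; a week-52 value after CRmin in treatment period 1 should not be planned.
- State which quantiles are meant, and give each a 95% confidence interval.

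In SAP section 8, add a figure list with the Kaplan-Meier curves and PDAI over time. If the sponsor prefers not to produce them, record that in SAP 6.1 as a change from Protocol 9.5.6.

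The cost is small. The estimates are standard output of a Kaplan-Meier analysis in SAS, the figures are few, and no new data are needed.

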9.5.7. Other Endpoints

argenx

Results from the exploratory research will not be part of the clinical database and will be described in a separate report.

9.5.8. Missing Data Handling

Details on handling missing data will be provided in the SAP.

9.6. Interim Analyses

Interim analyses may be performed in support of potential regulatory authority interactions.

9.7. Data Safety Monitoring Board

Refer to Section 10.1.5.

10. SUPPORTING DOCUMENTATION AND OPERATIONAL CONSIDERATIONS

10.1. Appendix 1: Regulatory, Ethical, and Study Oversight Considerations

10.1.1. Regulatory and Ethical Considerations

This study will be conducted in accordance with the protocol and with the following:

- Consensus ethical principles derived from international guidelines including the Declaration of Helsinki and Council for International Organizations of Medical Sciences (CIOMS) International Ethical Guidelines
- Applicable International Council for Harmonisation of Technical Requirements for Pharmaceuticals for Human Use (ICH) Good Clinical Practice (GCP) Guidelines
- Applicable laws and regulations

The protocol, protocol amendments, ICF, Investigator Brochure, and other relevant documents (eg, advertisements) must be submitted to an IRB/IEC by the investigator and reviewed and approved by the IRB/IEC before the trial is initiated.

Any amendments to the protocol will require IRB/IEC approval before implementation of changes made to the trial design, except for changes necessary to eliminate an immediate hazard to trial participants.

Protocols and any substantial amendments to the protocol will require health authority approval before initiation except for changes necessary to eliminate an immediate hazard to study participants.

The investigator will be responsible for the following:

- Providing written summaries of the status of the study to the IRB/IEC annually or more frequently in accordance with the requirements, policies, and procedures established by the IRB/IEC
- Notifying the IRB/IEC of SAEs or other significant safety findings as required by IRB/IEC procedures
- Providing oversight of the conduct of the study at the site and adherence to requirements of 21 CFR, ICH guidelines, the IRB/IEC, European regulation 536/2014 for clinical studies (if applicable), and all other applicable local regulations

10.1.2. Financial Disclosure

The sponsor will fund the study as outlined in the clinical study agreement.

The sponsor will obtain adequate global/local insurance for the study participants including the study participants for the required duration of time.

The sponsor maintains an insurance coverage for this study in accordance with the laws and regulations of the countries in which the study is performed. Liability and insurance provisions for this study are specified in the investigator's contract. The terms and conditions will apply as specified in the policy document.

10.1.3. Informed Consent Process

Before signing the ICF, the study participants will be instructed not to participate in any other clinical study that involves an intervention or collection of data until the completion of the current study.

Any participant who provides informed consent is being assigned a unique participant ID via the IRT system.

The investigator or his/her representative will explain the following to the participant and answer all questions regarding the trial: the nature of the study, its purpose, the procedures involved, the expected duration, any potential discomfort, potential alternative procedure(s) or course(s) of treatment available, and the extent of maintaining confidentiality of the participant's records.

Participants must be informed that their participation is voluntary, that they may withdraw from the study at any time, and that withdrawal of consent will not affect their subsequent medical treatment or relationship with the treating physician.

Participants will be required to sign a statement of informed consent, after receipt of detailed information on the study, that meets the requirements of 21 CFR 50, local regulations, ICH guidelines, Health Insurance Portability and Accountability Act requirements, where applicable, and the IRB/IEC or study center.

The ICF will be used to explain the potential risks and benefits of study participation to the participant in simple terms before the participant is screened.

A separate ICF will be issued in case of pregnancy of a female partner of a male participant.

The ICF contains a statement that the consent is freely given.

argenx

All participant information and ICFs must be available in the local and vernacular languages required at the site and include participant information sheets/brochures that outline the study procedures. All ICF(s) must be signed and dated by the participant.

Confirmation of a participant's informed consent must also be documented in the participant's medical record before any study-related procedure under this protocol, including screening tests and assessments. The authorized person obtaining the informed consent must also sign the ICF.

The investigator is responsible for ensuring that the informed consent is obtained from each participant and for obtaining the appropriate signatures and dates on the informed consent

document before the performance of any protocol procedures and before the administration of IMP.

Participants must be re-consented to the most current version of the ICF(s) during their participation in the study.

A signed and dated copy of the ICF(s) must be provided to the participant.

10.1.4. Data Protection

Participants will be assigned a unique identifier by the sponsor. Any participant records or datasets that are transferred to the sponsor will contain the identifier only; participant names or any information which would make the participant identifiable will not be transferred.

The participant must be informed that his/her personal study-related data will be used by the sponsor in accordance with local data protection law. The level of disclosure must also be explained to the participant who will be required to give consent for their data to be used as described in the informed consent

The participant must be informed that his/her medical records may be examined by Clinical Quality Assurance auditors or other authorized personnel appointed by the sponsor, by appropriate IRB/IEC members, and by inspectors from regulatory authorities.

Photography is generally accepted as routine practice for documenting dermatological conditions in medical practice. Photographs will be taken only at baseline for participants not in CR or with a flare and at subsequent visits to document response and progression. Participants will be requested to provide consent for any use that will be made of the image and for sharing anonymized pictures with the sponsor.

The ICF will incorporate (or, in some cases, be accompanied by a separate document incorporating) wording that complies with relevant data protection and privacy legislation.

10.1.5. Committees Structure

10.1.5.1. Data Safety Monitoring Board

The sponsor will appoint an independent DSMB consisting of an independent group of clinical experts who are not involved in the study management. They will be supplemented by an independent statistician. The DSMB may unblind the data collected during ARGX-113-1904, for the sake of the participant's safety in the study.

The objective of the DSMB will be to review all unblinded safety data (including the overall number of participants treated up to that point, rates, and participant-level details) and the evaluation of IgG. The planning and frequency of the meetings will be detailed in a DSMB charter. In addition, ad hoc meetings can be requested at any time during the study by either the sponsor or the DSMB. The DSMB will advise the sponsor regarding continuation, modification, or termination of the study after every meeting.

Additionally, the composition, objectives, role, and responsibilities of the independent DSMB will be described in the DSMB charter, agreed with the DSMB members and the sponsor. The DSMB charter will also define and document the content of the safety summaries and general procedures (including communications).

10.1.6. Dissemination of Clinical Study Data

The sponsor or designee, and auditor may access participant records for the purpose of monitoring this study, auditing, and managing progress details. The investigator must be fully aware that the sponsor or designee and auditor can inspect documents to verify the accuracy and completeness of a participant's chart and eCRF records. Such information must be kept confidential in locked facilities that allow for this level of protection. The investigator will prepare and maintain adequate and accurate source documents to record all observations and other pertinent data for each participant enrolled into the study.

The investigator is responsible for maintaining source documents. These will be made available for verification by the sponsor's designated CRO monitor at each monitoring visit. The investigator must submit an eCRF for each participant, regardless of duration of participation or administration of IMP. All supportive documentation submitted with the eCRF, such as laboratory or hospital records, should be clearly identified with the study and participant number. Any personal information, including participant name, should be removed or rendered illegible to preserve data privacy.

10.1.7. Data Quality Assurance

All participant data relating to the study will be recorded on printed or electronic CRF unless transmitted to the sponsor or designee electronically (eg, laboratory data). The investigator is responsible for verifying that data entries are accurate and correct by physically or electronically signing the eCRF.

The investigator must maintain accurate documentation (source data) that supports the information entered on the eCRF. Only if requested per local regulations, no source data verification will be performed on race and ethnicity.

The investigator must permit study-related monitoring, audits, IRB/IEC review, and regulatory agency inspections and provide direct access to source data documents.

Monitoring details describing strategy (eg, risk-based initiatives in operations and quality such as Risk Management and Mitigation Strategies and Analytical Risk-Based Monitoring), methods, responsibilities and requirements, including handling of noncompliance issues and monitoring techniques (central, remote, or on-site monitoring) are provided in the monitoring plan.

The sponsor or designee is responsible for the data management of this study including quality checking of the data.

The sponsor assumes accountability for actions delegated to other individuals (eg, CROs).

Study monitors will perform ongoing source data verification to confirm that data entered into the eCRF by authorized site personnel are accurate, complete, and verifiable from source documents; that the safety and rights of participants are being protected; and that the study is being conducted in accordance with the currently approved protocol and any other study agreements, ICH GCP, and all applicable regulatory requirements.

10.1.7.1. Data Handling and Record Keeping

It is the investigator's responsibility to maintain essential study documents (records and documents pertaining to the conduct of this study and the distribution of IMP, including regulatory documents, eCRFs, signed participant ICFs, laboratory test results, IMP inventory records, source documents, relevant correspondence, AE reports, and all other supporting documentation) as required by the applicable national regulatory requirements. The study site should plan on retaining such documents for approximately 25 years after study completion. The study site should retain such documents until at least 2 years after the last approval of a marketing application in an ICH region and until there are no pending or contemplated marketing applications in an ICH region, or at least 2 years after the formal discontinuation of clinical development of the IMP. The sponsor will notify the principal investigator of these events.

These documents should be retained for a longer period if required by the applicable regulatory requirements or the hospital, institution, or private practice in which the study is being conducted. Participant identification codes (participant names and corresponding study numbers) will be retained for this same period of time. These documents may be transferred to another responsible party, acceptable to the sponsor, who agrees to abide by the retention policies. The investigator is required to notify the sponsor (or an authorized representative) in writing before changing the location or status of any essential clinical study documents. The investigator must contact the sponsor before disposing of any study records.

No records should be disposed without the written approval of the sponsor, argenx BV.

For studies conducted outside the US under an US investigational new drug (IND), the principal investigator must comply with US Food and Drug Administration IND regulations and with those of the relevant national and local health authorities.

